## 8.2. Patient Exclusion Criteria

Patients meeting any of the following exclusion criteria are not eligible to participate in the study:

1. Treatment with a complement inhibitor at any time
2. Platelet count  $< 30,000/\text{mm}^3$  ( $30 \times 10^9 /\text{L}$ ) at screening
3. Absolute neutrophil count  $< 500/\mu\text{L}$  ( $0.5 \times 10^9 /\text{L}$ ) at screening
4. History of bone marrow transplantation
5. History of *N. meningitidis* infection or history of unexplained, recurrent infection
6. Female patients who are planning to become pregnant, or are pregnant or breastfeeding
7. Positive pregnancy test at screening or Day 1
8. Patients are excluded if they are taking any of the following medications and are not on a stable regimen (as judged by the Investigator) for the time period indicated prior to screening:
  - a. Erythropoietin or immunosuppressants for at least 8 weeks
  - b. Corticosteroids for at least 4 weeks
  - c. Vitamin K antagonists (eg, warfarin) with a stable international normalized ratio (per Investigator discretion) for at least 4 weeks
  - d. Iron supplements or folic acid for at least 4 weeks
  - e. Low molecular weight heparin for at least 4 weeks
9. Human immunodeficiency virus (HIV) infection (evidenced by HIV-1 or HIV-2 antibody titer)
10. Acute or chronic hepatitis B virus infection (evidenced by the presence of hepatitis B surface antigen or immunoglobulin M antibodies against hepatitis B core antigen).

11. Acute or chronic hepatitis C virus infection (evidenced by hepatitis C virus antibody)
12. Active systemic bacterial, viral, or fungal infection within 14 days prior to dosing on Day 1
13. Immunization with a live-attenuated vaccine 1 month prior to dosing on Day 1
14. Participation in an interventional clinical study within 30 days before initiation of dosing on Day 1, or use of any experimental therapy within 30 days prior to dosing on Day 1, or within 5 half-lives of the investigational product, whichever is greater
15. Major surgery within 90 days prior to dosing on Day 1
16. Presence of fever  $\geq 38$  °C within 2 weeks prior to the first dosing on Day 1
17. Patients with a history of malignancy within 5 years of screening with the exception of a nonmelanoma skin cancer or carcinoma in situ of the cervix that has been treated with no evidence of recurrence.
18. Known history of severe allergic or anaphylactic reactions to any drug (including vaccines) or allergen
19. History of allergy to excipients of ALXN1210 (eg, polysorbate 80)
20. Known allergy to Chinese hamster ovary cell proteins
21. History of any clinically significant cardiac, hepatic, immunologic, pulmonary, or rheumatoid disease that, in the Investigator's judgment, would preclude participation
22. Inability to comply with study requirements
23. Other unspecified reasons that, in the opinion of the Investigator or Sponsor, make the patient unsuitable for enrollment

### **8.3. Patient Withdrawal Criteria**

A patient may withdraw from the study at any time at his/her own request, or may be withdrawn at any time at the discretion of the Investigator. Patients who discontinue dosing will be instructed to return for follow-up visits, as described in the Schedule of Assessments ([Section 7](#)), unless they withdraw consent and/or are lost to follow-up.

- If the patient withdraws consent, the Early Termination visit should be completed as soon as possible.
- If the patient is withdrawn from ALXN1210, the Early Termination visit should occur prior to initiation of complement-targeted therapy.
- If the patient is withdrawn from ALXN1210, the patient should be encouraged to return for the remainder of his or her scheduled protocol visits until starting a different complement-targeted therapy.

Patients should be permanently discontinued from ALXN1210 treatment if any of the following occur during the study:

- Serious infusion reaction (such as bronchospasm with wheezing or requiring ventilator support or symptomatic hypotension, refer to [Section 9.1](#)) or serum sickness-like reactions manifesting 1 to 14 days after drug administration;
- Severe uncontrolled infection;
- Pregnancy or planned pregnancy; or
- If the Alexion medical monitor or the Investigator deem it is in the best interest of the patient.

## 9. TREATMENT OF PATIENTS

### 9.1. Management of Potential Drug Infusion Reactions

Some patients treated with IV infusions of mAbs have experienced concurrent infusion-related reactions with signs or symptoms that can be classified as acute allergic reactions/hypersensitivity reactions or cytokine release syndrome. The signs and symptoms include headache, fever, facial flushing, pruritus, myalgia, nausea, chest tightness, dyspnea, vomiting, erythema, abdominal discomfort, diaphoresis, shivers, hypertension, lightheadedness, hypotension, palpitations, and somnolence. Anaphylaxis might occur at any time during an infusion and patients will be monitored closely prior to and through 1 hour following the end of the infusion of ALXN1210. All AEs which may indicate an infusion-related response will be graded according to criteria from the National Cancer Institute Common Terminology Criteria for Adverse Events (CTCAE) v4.0.3.

Before infusion is started, the treating physician and other appropriate personnel, medication (adrenaline, inhaled beta agonists, antihistamines, and corticosteroids), and other requirements to treat anaphylaxis must be readily available.

The infusion will be stopped immediately if  $\geq$  Grade 2 allergic/hypersensitivity reaction (including drug fever) or  $\geq$  Grade 3 cytokine release syndrome/acute infusion reaction occurs. Alexion must be notified within 24 hours of any infusion reaction requiring interruption of study drug.

Patients experiencing a reaction during the administration of study drug should be treated according to institutional guidelines.

For a Grade 1 or Grade 2 infusion-related reaction, the infusion should be stopped, and medication with antihistamine (eg, with diphenhydramine, 25 to 50 mg orally or equivalent) and acetaminophen (650 mg orally or equivalent) may be considered. If the signs and symptoms have resolved with the above medications, the infusion may be restarted. If the infusion is slowed, the total infusion time should not exceed 5 hours, including any interruptions for safety or technical reasons. The study drug should be stopped if the infusion reaction recurs. Patients experiencing an infusion reaction should be observed in the clinic until resolution of the reaction, or in the Investigator's best judgment.

If an event of anaphylaxis occurs, according to the criteria listed in [Table 12](#) then subcutaneous epinephrine (1/1000, 0.3 to 0.5 mL or equivalent) should be considered. In the case of bronchospasm, inhaled beta agonist also should be considered. Patients administered antihistamine for the study drug or prevention of infusion reactions should be given appropriate warnings about drowsiness and impairment of driving ability prior to discharge.

Patients who experience a severe reaction during administration of study drug resulting in discontinuation of study drug should undergo all scheduled safety, PK, and PD evaluations required by the protocol.

**Table 12: Clinical Criteria for Diagnosing Anaphylaxis**

|  |
|--|
| Anaphylaxis is highly likely when any one of the following 3 criteria are fulfilled:  |
| 1. Acute onset of an illness (minutes to several hours) with involvement of the skin, mucosal tissue, or both (eg, generalized hives, pruritus or flushing, swollen lips-tongue-uvula) |
| AND AT LEAST ONE OF THE FOLLOWING:  |
| a. Respiratory compromise (eg, dyspnea, wheeze-bronchospasm, stridor, reduced PEF, hypoxemia)  |
| b. Reduced BP or associated symptoms of end-organ dysfunction (eg, hypotonia [collapse], syncope, incontinence)  |
| 2. Two or more of the following that occur rapidly after exposure to a likely allergen for that patient (minutes to several hours):  |
| a. Involvement of the skin-mucosal tissue (eg, generalized hives, itch-flush, swollen lips-tongue-uvula)   |
| b. Respiratory compromise (eg, dyspnea, wheeze-bronchospasm, stridor, reduced PEF, hypoxemia)  |
| c. Reduced BP or associated symptoms (eg, hypotonia [collapse], syncope, incontinence)   |
| d. Persistent gastrointestinal symptoms (eg, crampy abdominal pain, vomiting)  |
| 3. Reduced BP after exposure to known allergen for that patient (minutes to several hours):  |
| a. Systolic BP of less than 90 mm Hg or greater than 30% decrease from that person's baseline  |

Abbreviations: BP = blood pressure; PEF = peak expiratory flow

Source: Adapted from [Sampson, 2006](#)

## 9.2. Infection Risk

Due to its mechanism of action, the use of ALXN1210 increases the patient's susceptibility to meningococcal infection (*N. meningitidis*). Patients might be at risk of disease by uncommon serogroups (such as X), although meningococcal disease due to any serogroup may occur. To reduce the risk of infection, all patients must be vaccinated prior to receiving ALXN1210. Patients who are treated with ALXN1210 less than 2 weeks after receiving a meningococcal vaccine must receive treatment with appropriate prophylactic antibiotics until 2 weeks after vaccination. Vaccines against serotypes A, C, Y, W135, and B, where available, are recommended to prevent common pathogenic meningococcal serotypes. Patients must be vaccinated or revaccinated according to current national vaccination guidelines or local practice for vaccination use with complement inhibitors (eg, eculizumab).

Vaccination may not be sufficient to prevent meningococcal infection. Consideration should be given per official guidance and local practice on the appropriate use of antibacterial agents. All patients should be monitored for early signs of meningococcal infection, evaluated immediately if infection is suspected, and treated with appropriate antibiotics, if necessary.

To increase risk awareness and promote quick disclosure of any potential signs or symptoms of infection experienced by the patients during the course of the study, patients will be provided a safety card to carry with them at all times. Additional discussion and explanation of the potential

risks, signs, and symptoms will take place at specific time points as part of the review of the patient safety card and throughout the study as described in the Schedule of Assessments (Section 7).

### **9.3. Prior and Concomitant Medications and Procedures**

Prior medications (including vitamins and herbal preparations), including those discussed in the exclusion criteria (Section 8.2) and/or procedures (any therapeutic intervention, such as surgery/biopsy or physical therapy) the patient takes or undergoes within 28 days (or 3 years for documentation of meningococcal vaccination) prior to signing the informed consent form (ICF) until the first dose of ALXN1210 will be recorded on the patient's electronic case report form (eCRF).

All medication use during the study will be recorded in the patient's source/chart and eCRF. This record will include all prescription drugs, herbal products, vitamins, minerals, over-the-counter medications, and current medications for PNH. Any changes in concomitant medications also will be recorded in the patient's source/chart and eCRF. Any concomitant medication deemed necessary for the patient's standard of care treatment during the study, or for the treatment of any AE, along with the allowed medications described below may be given at the discretion of the Investigator. However, it is the responsibility of the Investigator to ensure that details regarding the medication are recorded in full in the patient's source/chart.

The following concomitant medications are allowed if the following apply, and dose adjustments are not expected during the Treatment Period:

- Patients are taking erythropoietin on a stable dose for at least 8 weeks prior to screening.
- Patients are taking immunosuppressants on a stable dose for at least 8 weeks prior to screening.
- Patients are taking corticosteroids on a stable dose for at least 4 weeks prior to screening.
- Patients are allowed to take vitamin K antagonists (eg, warfarin) but must have had a stable international normalized ratio level (per Investigator discretion) for 4 weeks prior to screening.
- Patients are taking iron supplements or folic acid on a stable dose for at least 4 weeks prior to screening.
- Patients are allowed to take low molecular weight heparin on a stable dose for at least 4 weeks prior to screening.

Adjustments in the frequency or level of dosing in any of the above medications can be made if the Alexion medical monitor or the Investigator deems it is in the best interest of the patient.

### **9.4. Treatment Compliance**

Patients will be administered ALXN1210 in a controlled setting under the Investigator's supervision, thereby ensuring compliance with ALXN1210 administration. Study coordinators at

the investigative site will ensure that all patients are adequately informed on the specific ALXN1210 dosing regimen required for compliance with the study protocol.

Alexion or its designee will periodically monitor study sites to ensure compliance with the protocol, and communicate with sites on a regular basis regarding study protocol deviations. All protocol deviations will be appropriately documented by the Investigator or designee and study monitors.

Unless otherwise specified, procedures, data collection, and evaluation will be conducted as per the clinical site's standard operating procedures.

## **9.5. Randomization and Blinding**

This is an open-label study. Up to 26 patients will be enrolled in the study. The first 2 eligible patients who meet the inclusion/exclusion criteria will be assigned to Cohort 1. The DMC will conduct a review of the available safety data as described in [Section 6.3](#) to determine whether the next cohort may be opened. If additional patients are screened and are eligible for enrollment before a dose-escalation decision has been made by the DMC for any cohort, those patients will be assigned to the active cohort with the lowest dose level.

## 10. STUDY DRUG MATERIALS AND MANAGEMENT

### 10.1. Description of Study Drug

ALXN1210 is formulated at 10 mg/mL and 100 mg/mL concentrations with a pH of 7.0 and 7.4, respectively (Table 13). Both ALXN1210 formulations are presented as sterile, preservative-free solutions for IV administration and are supplied in single-use vials. ALXN1210 will be provided by the Sponsor and is suitable for human use and manufactured under current Good Manufacturing Practices.

Further details are provided in the Investigator's Brochure and in the Pharmacy Manual.

**Table 13: Composition of Investigational Product**

| Name of Ingredient         | 10 mg/mL Concentration (IV)          | 100 mg/mL Concentration (IV)         | Function                         |
|----------------------------|--------------------------------------|--------------------------------------|----------------------------------|
| ALXN1210 antibody          | 10 mg/mL                             | 100 mg/mL                            | Active Ingredient                |
| Sodium phosphate monobasic | 3.34 mM 
(0.46 mg/mL) | 33.1 mM 
(4.42 mg/mL) | Buffering Agent                  |
| Sodium phosphate dibasic   | 6.63 mM 
(1.78 mg/mL) | 16.5 mM 
(4.42 mg/mL) | Buffering Agent                  |
| Sodium chloride            | 150 mM
(8.77 mg/mL)               | NA                                   | Tonicity                         |
| L-Arginine                 | NA                                   | 25 mM
(4.33 mg/mL)                | Stabilizer                       |
| Sucrose                    | NA                                   | 50 mg/mL                             | Tonicifying agent and stabilizer |
| Polysorbate 80             | 0.02% w/v                            | 0.05% w/v                            | Surfactant                       |
| Water for Injection        | QS                                   | QS                                   | Solvent                          |

Abbreviations: IV = intravenous; NA = not applicable; QS = quantum sufficiat (sufficient quantity).

 The sodium phosphate concentration is approximately 10 mM, which is comprised of sodium phosphate monobasic and the sodium phosphate dibasic.

 The sodium phosphate concentration is approximately 50 mM, which is comprised of sodium phosphate monobasic and the sodium phosphate dibasic.

### 10.2. Study Drug Packaging and Labeling

ALXN1210 will be supplied in a one-vial-per-kit configuration. Each vial and carton will be labeled according to specific country or region regulatory requirements.

### 10.3. Study Drug Storage

ALXN1210 vials must be stored in refrigerated conditions at 2°C to 8°C (36°F to 46°F) and protected from light. ALXN1210 vials should not be frozen or shaken.

### 10.4. Study Drug Preparation

Preparation of ALXN1210 doses must be performed in accordance with site-specific local standards by qualified and study-trained pharmacy personnel.

Handling and preparation of materials used to prepare and administer study drug must be carried out using aseptic techniques for sterile products.

Pharmacy personnel will prepare doses in accordance with the dose assignment.

Please refer to the Pharmacy Manual for additional dose preparation instructions.

#### 10.4.1. ALXN1210 Dose Preparation

ALXN1210 will be diluted in 0.9% sodium chloride injection (country-specific pharmacopeia) and administered by IV infusion at a fixed rate by dose, as indicated in [Table 14](#).

For each patient, doses will be prepared as required for each dose cohort, as indicated in [Table 14](#).

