**Table 14: Dosing Reference Chart for 10 mg/mL ALXN1210 Formulation Dose Preparation**

| Dose (mg) | Infusion Volume (mL) | Maximum Infusion Rate (mL/hour) | Minimum Infusion Duration minutes (hours) |
|-----------|----------------------|---------------------------------|---|
| 1000      | 200                  | 333                             | 36.0 (0.6)                                |
| 1400      | 280                  | 333                             | 50.4 (0.8)                                |
| 1600      | 320                  | 333                             | 57.6 (1.0)                                |
| 2000      | 400                  | 333                             | 72.1 (1.2)                                |
| 2400      | 480                  | 333                             | 86.4 (1.4)                                |
| 3000      | 600                  | 333                             | 108.1 (1.8)                               |
| 5400*     | 1080                 | 333                             | 194.6 (3.2)                               |

\*To be given in divided dose.

Please refer to the Pharmacy Manual for additional dose preparation instructions.

These dosing rates apply to patients  $\geq 50$  kg; for patients  $< 50$  kg, please refer to the pharmacy manual.

Beginning on Day 463 for patients in Cohort 2, Day 477 for patients in Cohorts 3, and Day 533 for patients in Cohort 1, patients will switch from their current dose regimen to a q8w, weight-based regimen, as shown in [Table 15](#). The dose regimen will not change for patients in Cohort 4.

**Table 15: Weight-based Dosing Reference Chart for 10 mg/mL ALXN1210 Formulation Dose Preparation Beginning on Day 463 (Cohort 2), Day 477 (Cohort 3), and Day 533 (Cohort 1)**

| Body Weight (kg) a | Dose (mg) | ALXN1210 Volume (mL) | Total Volume (mL) | Maximum Infusion Rate (mL/hr) | Minimum Infusion Duration in minutes (hr) |
|-------------------------------|-----------|----------------------|-------------------|-------------------------------|---|
| $\geq 40$ to $< 60$           | 3000      | 300                  | 600               | 250                           | 140 (2.4)                                 |
| $\geq 60$ to $< 100$          | 3300      | 330                  | 660               | 330                           | 120 (2.0)                                 |

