| $\geq 100$                    | 3600      | 360                  | 720               | 328                           | 132 (2.2)                                 |

Note: For patients weighing  $< 40$  kg, please see Pharmacy Manual.

a Dose regimen will be based on the last recorded study visit body weight. If the study drug is prepared the night before a visit, the weight from the most recent study visit should be used.

Beginning on Day 953 for patients in Cohort 4, Day 981 for patients in Cohort 3, Day 1023 for patients in Cohort 2, and Day 1037 for patients in Cohort 1, patients will switch from the 10 mg/mL ALXN1210 unit dose formulation to the 100 mg/mL ALXN1210 unit dose formulation ([Table 16](#)), while remaining on their current dose regimen.

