**Table 16: Dosing Reference Chart for 100 mg/mL ALXN1210 Formulation Dose Preparation**

| Dose (mg) | ALXN1210 Volume (mL) | Total Volume (mL) | Maximum Infusion Rate (mL/hour) | Minimum Infusion Duration minutes (hours) |
|-----------|----------------------|-------------------|---------------------------------|---|
| 3000      | 30                   | 60                | 65                              | 55 (0.92)                                 |
| 3300      | 33                   | 66                | 98                              | 40 (0.67)                                 |
| 3600      | 36                   | 72                | 144                             | 30 (0.50)                                 |
| 5400      | 54                   | 108               | 67                              | 95 (1.6)                                  |

Please refer to the Pharmacy Manual for additional dose preparation instructions.

These dosing rates apply to patients  $\geq 50$  kg; for patients  $< 50$  kg, please refer to the Pharmacy Manual.

Please refer to the Pharmacy Manual for additional dose preparation instructions.

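### Protocol Section 10.4.1: infusion rates and minimum durations disagree within two table rows, and the lead sentence names only one of the three tables that apply

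*Protocol*

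**What the plan says.** Protocol Section 10.4.1 states that the drug is "administered by IV infusion at a fixed rate by dose, as indicated in" Table 14, and points to the same table for preparing each cohort's doses. Three tables follow. The rows below are quoted as printed, ending with the minimum duration in minutes and, in brackets, in hours; the closing bracket is cut off.

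- Table 14 (10 mg/mL product) gives dose, infusion volume, maximum rate and minimum duration. Every dose has the same 333 mL/h maximum. The 3000 mg row reads "3000 | 600 | 333 | 108.1 (1.8".
- Table 15 (10 mg/mL product, weight-based) gives dose, drug volume, total volume, maximum rate and minimum duration. It applies to Cohorts 2, 3 and 1 from Days 463, 477 and 533. The rows read "3000 | 300 | 600 | 250 | 140 (2.4" for 40 to under 60 kg, "3300 | 330 | 660 | 330 | 120 (2.0" for 60 to under 100 kg, and "3600 | 360 | 720 | 328 | 132 (2.2" for 100 kg and above.
- Table 16 (100 mg/mL product) applies from Day 953 to Day 1037, depending on cohort. Its 3000 mg row reads "3000 | 30 | 60 | 65 | 55 (0.92" and its 5400 mg row "5400 | 54 | 108 | 67 | 95 (1.6".

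The weight notes differ. Under Table 16 the note begins "These dosing rates apply to patients" and sets the limit at 50 kg, sending lighter patients to the Pharmacy Manual; Table 14 carries the same note. Table 15 sends only patients under 40 kg to the manual. Section 10.5 refers to Section 10.4.1 for rates and to the Pharmacy Manual for volume and duration.

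**The concern.** For a given volume, a maximum rate and a minimum duration express the same limit, so they should agree. If the printed minutes are shorter than volume divided by rate, an infusion that meets the duration limit can still exceed the rate limit. Section 9.1 treats infusion reactions as a recognised risk of this drug class, so these are working figures for giving study drug.

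The sentence introducing the tables adds to the uncertainty. It calls the rate fixed, whereas the columns are maxima. It names Table 14 only, although two other tables take over later. At stake are clear instructions to sites and a clean basis for deciding what counts as a dosing deviation. The efficacy inference is not at stake.

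**Working it through.** **Inputs.** Volumes, maximum rates and printed durations come from Protocol Tables 14, 15 and 16.

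**Formulas.** Duration at the cap (min) = volume ÷ maximum rate × 60. Rate implied by the printed duration (mL/h) = volume ÷ (printed minutes ÷ 60).

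**Reproducing the plan's figures.** All seven rows of Table 14 agree with 333 mL/h to within 0.1%; two are shown, with every row of Tables 15 and 16.

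| Table | Dose (mg) | Volume (mL) | Max rate (mL/h) | Printed min | Min at the cap | Implied mL/h | Against cap |
|---|---|---|---|---|---|---|---|
| 14 | 3000 | 600 | 333 | 108.1 | 108.1 | 333.0 | 0.0% |
| 14 | 5400 | 1080 | 333 | 194.6 | 194.6 | 333.0 | 0.0% |
| 15 | 3000 | 600 | 250 | 140 | **144.0** | **257.1** | **+2.9%** |
| 15 | 3300 | 660 | 330 | 120 | 120.0 | 330.0 | 0.0% |
| 15 | 3600 | 720 | 328 | 132 | 131.7 | 327.3 | −0.2% |
| 16 | 3000 | 60 | 65 | 55 | 55.4 | 65.5 | +0.7% |
| 16 | 3300 | 66 | 98 | 40 | 40.4 | 99.0 | +1.0% |
| 16 | 3600 | 72 | 144 | 30 | 30.0 | 144.0 | 0.0% |
| 16 | 5400 | 108 | 67 | 95 | **96.7** | **68.2** | **+1.8%** |

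**Can rounding explain the two bold rows?**

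- *Table 15, 3000 mg.* No. To the nearest minute the figure is 144, and to the nearest 5 minutes it is 145. The cell also disagrees with itself: 140 ÷ 60 = 2.33 h, but 2.4 h is printed, and 2.4 × 60 = 144.
- *Table 16, 5400 mg.* Not to the nearest minute (97). It does fit rounding to the nearest 5 minutes, as do the other three rows (55.4 to 55, 40.4 to 40, 30.0 to 30). But rounding a minimum duration down lets the implied rate pass the stated maximum, and the 3000 and 3300 mg rows do this too, by about 1% at most.

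**Lead sentence against the tables.** Table 14 has no 3300 mg or 3600 mg row, so it cannot govern the weight-based doses. Tables 15 and 16 do, by cohort and day. All three tables head the column as a maximum, not a fixed rate.

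**Same dose and volume, two caps.** 3000 mg in 600 mL of the 10 mg/mL product carries 333 mL/h in Table 14 and 250 mL/h in Table 15: 333 ÷ 250 = 1.33, or 33% higher. Under the dosing schedule (Protocol Table 3), the Table 14 row is needed only for Cohort 4 on Day 1, at 50 kg or more. The Table 15 row is for Cohorts 1 to 3 from Day 463 or later, at 40 to under 60 kg. The two rows share a weight range (50 to under 60 kg) but no patients. No reason for the difference is stated.

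**Weight limits.** For 40 to under 50 kg on 3000 mg, Table 15 prints a rate, while Table 16, which lists the same dose, refers the site to the Pharmacy Manual.

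**The case against.** A site that observes both columns of the right table cannot exceed the cap: 144 min satisfies a 140 min minimum, and 96.7 min satisfies 95. Section 10.5 takes rates from Section 10.4.1 but leaves duration to the Pharmacy Manual, so a pump set from the printed minutes is not the route the protocol describes. Table 16 follows a consistent 5-minute rounding. In Table 15 only the minutes entry is out of line with the other two figures in its row. The text after the lead sentence does direct readers to Tables 15 and 16 by cohort and day. Caps may also differ deliberately: the 250 mL/h row has to cover patients down to 40 kg, whereas Table 14 stops at 50 kg.

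This makes the point small but does not remove it. The Table 15 cell remains internally inconsistent, a minimum duration should not imply a rate above the stated maximum, and the 333/250 difference remains unexplained.

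A reader might infer more than the documents support:

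- *One patient has two caps for the same bag, or two sites could treat the same patient differently while both comply.* No patient falls under both 3000 mg rows. Cohort 4 never moves to Table 15, and Cohorts 1 to 3 never receive 3000 mg under Table 14. A Table 15 patient would meet 333 mL/h for that dose only if a site took the lead sentence literally and ignored Table 15.
- *End-of-infusion PK samples are distorted by Tables 15 and 16.* Protocol Table 17 schedules only predose samples in the Extension Period, plus one at discontinuation or the last visit.
- *The 40/50 kg mismatch leaves patients uncovered or permits a faster rate.* Below the cut-off, sites are sent to the Pharmacy Manual. Without that manual no rate conflict can be shown.

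**Conclusion.** The figures are wrong as written, at minor severity. The firmest error is the Table 15 3000 mg row, where 140 min conflicts with both the 250 mL/h maximum and the 2.4 h beside it: 4 min short, or 2.9% over the cap. The Table 16 5400 mg row is 1.7 min short, or 1.8% over, through downward rounding. The lead sentence is inaccurate in calling the rate fixed and incomplete in naming only Table 14. The 333 against 250 mL/h difference is unexplained, but it lies between patients of similar weight in different cohorts and periods. The differing weight cut-offs need explaining, no more than that.

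This rests on the printed volumes being infused in full at a constant rate, and on the protocol alone, since the Pharmacy Manual is not available. The documents do not show whether rate or duration is the wrong entry in either row. Tables 15 and 16 take effect after Day 253, and after Day 281, where the SAP (Section 4) ends its report for Cohort 4. Power, alpha and the primary analysis are therefore unaffected.

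**What to change.** 1. Reconcile rate, minutes and hours in the Table 15 3000 mg row and the Table 16 5400 mg row. No printed minimum duration should imply a rate above the printed maximum; check the Table 16 3000 and 3300 mg rows for the same reason.
2. Reword the opening of Section 10.4.1 so that it speaks of a maximum rate and names the table that applies to each cohort and period.
3. Reconcile the 333 and 250 mL/h caps for 3000 mg in 600 mL, and the 40 kg and 50 kg cut-offs, against the Pharmacy Manual, or state why they differ.

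Which rate, duration or cut-off is right is for the sponsor's clinical and pharmacy teams. The cost is wording in the protocol and, if needed, the manual. For the two rows in item 1, the gap to close is 4 min (144 − 140) and 1.7 min (96.7 − 95).
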